mAb monoclonal antibody

MAR missing at random

MCH mean cell hemoglobin

MCHC mean corpuscular hemoglobin concentration

MCMC Markov Chain Monte Carlo

MCV mean corpuscular volume

MedDRA Medical Dictionary for Regulatory Activities

MI Multiple Imputation

mITT modified Intent to Treat analysis set

MMRM mixed effect model for repeated measures

MNAR missing not at random

mRNA messenger ribonucleic acid

NAb neutralizing antibody

NCMV neighboring-case missing values

nMiss number of missing observations

NRCD non-responsive celiac disease

PCI potentially clinically important

PD pharmacodynamic(s)

PGIC Patient Global Impression of Change

PGIS Patient Global Impression of Severity

PK pharmacokinetic(s)

PP per protocol

PT Preferred Term

q2w every 2 weeks

QoL quality of life

RA rheumatoid arthritis

Rac accumulation ratio

RBC red blood cell count

RCD-II refractory celiac disease Type II

RIS Run-in analysis set

SAE serious adverse event

SAP Statistical Analysis Plan

SAS® Statistical Analysis System

SC subcutaneous(ly)

SD standard deviation

SMQ Standardized MedDRA query

SoA schedule of activities

SOC System Organ Class

SUSAR Suspected Unexpected Serious Adverse Reaction

TB tuberculosis

TEAE treatment-emergent adverse events

TIBC Total iron binding capacity

TNFa tumor necrosis factor alpha

tss Time at which 90% of the subject specific Css is achieved

tTG tissue transglutaminase

ULN upper limit of normal

UN unstructured

ULQ Upper limit of quantitation

VAS Visual analog scale

VH:CD villous height-to-crypt depth ratio

WBC white blood cell count

WOCBP women of childbearing potential

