where Y_i and Dose; are the C_{min} value and dose value for subject i, respectively, ϵ_i is the random error, α is the intercept parameter and β is the slope parameter. The power model parameters will be estimated using least -squares (LS) regression and presented with 90% CIs. Model lack-of-fit will be assessed by residual plots, and by an F-test of the residual mean square versus the pure error residual mean square. If the model fit is adequate, point estimate and 90% CI for β will be obtained, and used to obtain point estimates and 90% CIs for the increase in C_{min} associated with an r-fold (r=2 and r=high dose / low dose) increase in dose, by exponentiating r to the power of the β point estimate and confidence limits, $r^{\beta \pm t \times SE(\beta)}$. If there is evidence of model lack-of-fit, then an ANOVA model on the log-transformed C_{min} with dose as fixed categorical effect will be used. Point estimate and 90% CI, associated with mean difference between pairwise dose increases, obtained from this model will be converted back to the original scale using the antilog transformation.

Accumulation ratio:

For C_{min} , individual accumulation ratio Rac C_{min} at Day 169 will be calculated as C_{min} at Day 169/ C_{min} at Day 15. A listings of individual accumulation ratios will be provided, along with their descriptive statistics (arithmetic mean, standard deviation, geometric mean, coefficient of variation (%), median, minimum and maximum).

Accumulation versus Day 15 (Visit 4) will be assessed for Day 169 (Visit 15) using an ANOVA model on the log-transformed accumulation ratio (Rac C_{min}) with dose as fixed categorical effect. Point estimates and 90% CI obtained, by dose level and overall, from this model will be converted back to the original scale using the antilog transformation.

Achievement of steady-state:

Steady state on Cmin (ie, Ctrough) will be assessed using a nonlinear mixed model (Hoffman et al, 2005):

$$C_{ij} = C_{ss}e^{c_i}(1 - e^{-(\gamma e^{g_i}j)})e^{\varepsilon_{ij}}$$

where C_{ij} is the observed trough (C_{min}) plasma concentration for the ith subject on Day j, C_{SS} is the average steady state trough (C_{min}) plasma concentration, γ is the average first-order elimination rate, $\epsilon_{ij} \sim N(0, \sigma^2_e)$ is the random within-subject error, and c_i and g_i are the random individual deviations from C_{SS} and γ , respectively, such that

 $(c_i, g_i) \sim N([0, 0], \Sigma)$ with

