$$\Sigma = \begin{bmatrix} \sigma_c^2 & \sigma_{cg} \\ \sigma_{cg} & \sigma_g^2 \end{bmatrix}$$

The model assumes a log-normal distribution for both the within-subject erros (ϵ_{ij}) and the random effects c_i and g_i . The above nonlinear model analysis will be based on the log-transformed C_{min} values. Data from all subjects together from all dose groups will be used for the analysis.

Time (t_{ss} in days) at which 90% of the subject-specific C_{ss} is achieved (ie, individual steady state attainment) will be calculated from the model, using the equation:

$$t_{ss} = \frac{\log(1 - 0.9)}{-\gamma}$$

Similarly, time (in days) at which 50% of the subject-specific C_{ss} is achieved (ie, average steady state attainment) will also be provided.

In addition, model parameter estimates with standard errors and 90% CIs will be provided. The adequacy of the nonlinear model will be assessed graphically by plotting residual versus dose, residual versus time, and observed (log-scale) and predicted values versus time for individual subjects.

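### SAP 8.8.1.2 mislabels both steady-state times: the one called average is a half-life, and the one called individual is the typical-subject 90% time

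*SAP*

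**What the plan says.** SAP 8.8.1.2, under achievement of steady-state, models the trough of subject i on Day j as Css·exp(c_i)·(1 − exp(−γ·exp(g_i)·j)), times a log-normal error. Css is the average steady-state trough and γ "is the average first-order elimination rate". The terms c_i and g_i "are the random individual deviations from C_{SS} and γ , respectively", and are normal with mean zero.

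Two times are then planned:

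- The time "at which 90% of the subject-specific C_{ss} is achieved (ie, individual steady state attainment) will be calculated from the model". Its printed formula is log(1 − 0.9) divided by −γ.
- A second time, for which no formula is printed: "Similarly, time (in days) at which 50% of the subject-specific C_{ss} is achieved (ie, average steady state attainment) will also be provided".

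The SAP List of Abbreviations knows only the 90% criterion: "tss Time at which 90% of the subject specific Css is achieved". Model parameter estimates are to be given with standard errors and 90% CIs. Protocol 9.4.6 lists achievement of steady state, based on Cmin, among the planned PK assessments.

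**The concern.** Individual and average attainment should differ in whose rate is used: the subject's own, γ·exp(g_i), or the typical one, γ. They should not differ in the fraction of the plateau that counts as steady state. The SAP changes the fraction from 90% to 50% and leaves the rate alone. As a result, neither label matches its quantity.

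What is at stake is one line of the PK report. Someone looking for the average time to steady state would go to the line with that name and find one half-life. Someone looking for the individual times would find a formula with no individual term in it.

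**Working it through.** **Inputs** (all from SAP 8.8.1.2 unless noted)

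- Model for the trough: Css·exp(c_i)·(1 − exp(−γ·exp(g_i)·j)), with j in days.
- γ is the average elimination rate, so the half-life of the typical subject is ln2/γ.
- Criterion for attainment: 90% of subject-specific Css (also in the List of Abbreviations).
- Half-life of PRV-015: not given in the documents. Values of 7 to 28 days are assumed below for illustration only.

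**1. Fraction of plateau reached.** Subject-specific Css is Css·exp(c_i), so c_i cancels. Leaving error aside, the fraction reached at time t is 1 − exp(−γ·exp(g_i)·t). Setting this equal to f gives

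t_f = −ln(1 − f) / (γ·exp(g_i)).

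**2. Reproduce the SAP's formula.** With f = 0.9 and g_i = 0, t = −ln(0.1)/γ = 2.303/γ. This is the printed t_ss exactly, with log read as natural log. It matches only with g_i = 0, so the printed formula is the typical-subject time. The time for subject i would be 2.303/(γ·exp(g_i)).

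**3. The 50% time.** With f = 0.5 and g_i = 0, t = −ln(0.5)/γ = 0.693/γ = ln2/γ, which is one half-life. The trough is then at half its plateau by construction.

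**4. Ratio.** ln10/ln2 = 2.3026/0.6931 = 3.32. Both γ and g_i cancel, so the ratio is the same for every subject and any elimination rate.

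**5. In days, for assumed half-lives**

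| Assumed half-life | Time to 50% of Css | Time to 90% of Css |
|---|---|---|
| 7 days | 7.0 | 23.3 |
| 14 days | 14.0 | 46.5 |
| 21 days | 21.0 | 69.8 |
| 28 days | 28.0 | 93.0 |

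**6. Does another meaning of average rescue the 50% figure?** Take g_i normal with mean 0 and SD s. The SAP gives no s, so 0 to 0.7 is assumed.

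- Median of the individual 90% times: exp(g_i) has median 1, so the median is 2.303/γ for any s. The ratio to ln2/γ stays at 3.32.
- Mean of the individual 90% times, or the time at which the population-mean curve reaches 90%: by simulation, 3.4 to 4.4 times ln2/γ for s from 0.2 to 0.7.
- Share of subjects at 90% of their own Css by t = ln2/γ: this requires exp(g_i) ≥ 3.32, that is g_i ≥ 1.20. The share is 0% at s = 0, 0.8% at s = 0.5 and 4.3% at s = 0.7.

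No reading of average tried here brings the 90% time down to one half-life.

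**The case against.** The case on the other side is that this is wording, not arithmetic. No number is miscalculated, the one printed formula reproduces exactly, and the disputed sentence states openly that it concerns 50% of Css. The 90% time is the only one with a symbol and an equation, and the 50% time is an addition to it. The report will also hold troughs by time point, concentration-time plots, the Day 169 to Day 15 accumulation ratio and the model parameters, so a careful reader would not be misled for long. The individual and average wording may also come from the methods paper that the SAP cites, which is not available here, and 50% may be a slip for 50% of subjects.

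Most of this stands, and it limits the size of the point. It does not remove the mismatch. The sentence as written refers to 50% of the subject-specific plateau, and if 50% of subjects was meant, the answer would be the median of the individual 90% times, 2.303/γ. The missing exp(g_i) in the formula called individual is a separate inconsistency that none of these arguments addresses.

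A reader might infer more: that the SAP's steady-state result is itself 3.3 times too short, or that the error reaches the sampling schedule or the 24-week average of the primary endpoint. The documents do not support this. The 90% time is reported as t_ss. Sampling visits are fixed by the Schedule of Activities (Protocol 1.3, SAP 11.1). The primary model (SAP 8.6.1.2) uses Weeks 2 to 24 and takes no PK quantity as input.

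**Conclusion.** Wrong as written, and minor. The time labelled average attainment is one half-life, 3.32 times shorter than the time by the SAP's own 90% criterion. The time labelled individual attainment is the typical-subject 90% time. The factor of 3.32 follows from the stated model alone and needs no value for γ. It is relative to the 90% criterion and applies only to the 50% line, not to t_ss. The day counts rest on assumed half-lives, and the results for other meanings of average rest on assumed between-subject SDs. The consequence is a mislabelled descriptive PK result, with the correct 90% figure still available. The documents do not show which meaning of 50% was intended.

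**What to change.** Amend the two definitions in SAP 8.8.1.2 together. Changing only the 50% sentence to ln(10)/γ would print the same number twice, once as individual and once as average.

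- Label ln(10)/γ as average (typical-subject) steady-state attainment and give its 90% CI. With 90% limits γ_L and γ_U for γ, the interval is ln(10)/γ_U to ln(10)/γ_L.
- Define individual attainment as ln(10)/(γ·exp(g_i)), using each subject's predicted g_i, and summarise it across subjects by median and percentiles.
- Drop the time to 50% of Css, or label it as the time to half of steady state (half-life).
- If 50% was meant as 50% of subjects, say so and use the median of the individual 90% times.
- Align the definition of tss in the List of Abbreviations with whichever of the two times keeps that symbol.

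The cost is a few lines of SAP text and the matching table labels. Everything comes from the model fit already planned.

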8.8.2 Immunogenicity

Immunogenicity, i.e. the generation of ADA, will be tested in an immunoassay. Samples that test positive for binding antibodies will be then tested in an assay to detect neutralizing antibodies (NAb). Immunogenicity will be tabulated by treatment group, visit, ADA test result (negative, positive) and neutralizing antibodies test result (negative, positive) and listed using the IMG analysis set.

8.9 Interim Analyses and Data Monitoring

No formal interim analysis is planned for this study. An internal Data Monitoring Committee (DMC) evaluated risk-benefit continually during the study and did not recommend any changes to study conduct.

8.10 Changes in the Statistical Plans from Those Presented in the Study Protocol (if applicable)

The following list of changes are applicable to this SAP and differ from those presented in the study protocol:

- For general summaries of continuous values, Q1 and Q3 will be presented in addition to N, mean, SD, median, minimum, and maximum. Coefficient of variation (CV%) will not be presented for general summaries, but CV%_{geo} will be provided for PK-related summaries as described.
- The study protocol indicates that the primary efficacy model will test an AR(1) variancecovariance structure against the Unstructured variance-covariance structure using likelihood

ratio testing. The SAP removes this testing and instead provides a hierarchy of variance-covariance structures to use in the case of issues with model convergence.

- Change from baseline at 24 weeks for the CeD PRO Nausea domain has been added as an exploratory endpoint.
- The protocol specifies that exploratory clinical endpoints will be evaluated on the Per Protocol
 analysis set. This SAP indicates that only the primary and secondary efficacy endpoints will
 be evaluated on the Per Protocol analysis set; however, exploratory analyses may be
 conducted on the Per Protocol analysis set as necessary.
- Due to an unexpected change in laboratory platform, the tertiary Anti-TTG antibody IgA and Anti-DGP antibody IgA analyses will be limited to the subset of subjects who have all of their available samples analyzed via ELISA methods.
- The Protocol specifies that primary analysis will be done on ITT population, in this SAP mITT population has been defined and all efficacy analysis will be done on mITT population unless otherwise specified.

8.11 Execution of Statistical Analyses

Statistical analysis will be performed by IQVIA Biotech (formerly StatFinn) under the supervision of Provention Bio, Inc.

9 HARDWARE AND SOFTWARE

Statistical analysis, tables, figures and subject data listings will be performed with SAS® for Windows version 9.4 or higher (SAS Institute Inc., Cary, NC, USA).

11 APPENDICES

11.1 Schedule of Activities (SoA)

	Screening (≤28 Days)		-Blind Period				Doub	le-Blin	d Ran	domiz	ed Tre	atment	t Perio	d			Follow- up Visit
Visit #	Screen1	1	2	3	4	5	62	7	82	9	10 ²	11	122	13	14	15/ Early Term	16
Week	-8	-4	-2	0	2	4	6	8	10	12	14	16	18	20	22	24	28
Day	-56	-28	-14	1	15	29	43	57	71	85	99	113	127	141	155	169	197
Window (Days)			±2	+2	±2	±2	±2	±2	±2	±2	±2	±2	±2	±2	±2	±2	±7
Study Procedures																	
Informed consent	X																
Demographics	X																
Medical history	X				11			14. 1				1					
Physical examination ³	X	X	X	X	X	X		X		X		X		Х		X	X
Weight	X	X	X	X	X	X		X		X		X		X	7.1	X	X
Height	X				1.74												
Vital signs ⁴	x	x	X	X	X	X	X	X	X	X	X	X	X	X	X	X	X
12-lead ECG	X	1													- 1	-	
Blood and urine samples for clinical lab tests ⁵	X ⁶	х		х		x		x		x		x		x		х	х
H. pylori stool test	x	1													-		
Blood tests for ferritin, iron, TIBC, vitamins D, B12, folate				x			П			х						x	
Serum pregnancy test (WOCBP)	x																
LH/FSH (non-WOCBP)	X																
Urine pregnancy test (all WOCBP)		х	х	x		x		x		x		x		x		х	x
Stool and urine gluten test ⁷		x	х	x	x	x		x		x		x		x	71	x	X

	Screening (≤28 Days)		e-Blind Period				Doub	le-Blir	ıd Ran	domiz	ed Tre	atment	Perio	d			Follow- up Visit
Visit #	Screen ¹	1	2	3	4	5	62	7	82	9	102	11	122	13	14	15/ Early Term	16
Week	-8	-4	-2	0	2	4	6	8	10	12	14	16	18	20	22	24	28
Day	-56	-28	-14	1	15	29	43	57	71	85	99	113	127	141	155	169	197
Window (Days)			=2	+2	±2	±2	±2	±2	±2	±2	±2	±2	±2	±2	±2	±2	±7
Randomization				X													
Serum IgA test	X				-												
Serum for PK ⁸				X	X	X		X		X		X		X	X	X	X
Serum for ADA ⁸				X	X	X				X					X	X	X
Anti-tTG and anti-DGP antibodies ⁹	х			x		х		x		x		x		x		x	х
Serum for biomarkers ¹⁰				X	-	X		X		X		X		X		X	X
Eligibility confirmation	X			X		-		1								1	
Prior and concomitant medications	x	х	x	x	x	x	x	x	x	x	x	x	x	x	x	х	х
Study drug administration		X11	X11	x	x	x	x	x	x	x	x	x	x	x	x		
EGD and biopsy			X^{12}						-				E 4			X^{13}	
Stool frequency question ¹⁴		<															·>
CeD PRO15		<															·>
ICDSQ				X						X						X	
EQ-5D-5L				X						х	100					X	
Weekly diet stability questions		<						- William									·>
GSRS	X			+													
IGA		X	=	X	X	X		X		X		X		X		X	X
PGIC ¹⁶		1 = = 1	X	X	X	X	X	X	X	X	х	X	X	X	X	Х	X
PGIS ¹⁶		x	X	X	х	X	X	X	X	X	X	X	X	х	X	X	X
Assessment of adverse events ¹⁷	x	х	x	х	x	x	x	x	x	x	x	x	x	х	x	х	х

Abbreviations: ADA=anti-drug antibody; BP=blood pressure; BSFS=Bristol Stool Form Scale; CeD PRO=Celiac Disease Patient Reported Outcome; DGP=deamidated gliadin peptide; ECG=electrocardiogram; EGD=esophagogastroduodenoscopy; Early Term=early termination; FSH=follicle-stimulating hormone; GSRS=Gastrointestinal Symptom Rating Scale; HbA1C=hemoglobin A1C; HBV=hepatitis B virus; HCV=hepatitis C virus; HIV=human immunodeficiency virus; HLA=human leukocyte antigen; IGA=Investigator Global Assessment; LH=lutemizing hormone; PGIC=Patient Global Impression of Change: PGIS=Patient Global Impression of Severity: PK=pharmacokinetics; QoL=quality of life: TIBC=total iron binding capacity; tTG=tissue transglutaminase; WOCBP=women of childbearing potential, non-WOCBP=women not of childbearing potential.

- Testing for COVID-19 infection (including viral RNA testing for acute infection and/or antibody testing for past exposure) may be conducted if appropriate
- Visits 6, 8, 10, and 12 may be conducted remotely by certified mobile healthcare personnel per Investigator's decision.

 A complete physical examination is required at screening, Visit 1, Visit 15, and Visit 16. At other visits, the physical examinations are symptom directed.
- Vital signs (including temperature, BP, heart rate, and respiratory rate) will be measured prior to each study drug administration. Vital signs will be taken again 30 minutes after study drug administration.
- 5. Blood and urine samples will be collected for hematology, chemistry, and urinalysis. In addition, HbA1c should be measured in those subjects with diagnosis of Type 1 or Type 2 diabetes only. If glucose is detected in the urine, HbA1c should be tested and the subject should receive clinical evaluation for diabetes per standard of care.
- The screening blood samples include HIV, HBV, HCV, and IGRA tests. In addition, a test for HLA DQ2 and/or DQ8 typing will be performed if a previous report is not supplied.
- Stool gluten samples will be collected by the subject the day before each scheduled visit or during the visit (with a window of 3 days before or after the visit). Urine gluten samples will be collected at the time of the office visit.
- Blood samples for PK and ADA analyses should be collected before study drug administration (baseline) and at each visit before dosing (trough). The exact time and date of sample collection must be recorded. ADA analysis includes neutralizing antibodies (NAb). The anti-tTG and anti-DGP antibody tests at the screening visit will include both IgA and IgG. At all other visits, only anti-tTG IgA and anti-DGP IgA will be
- 10. Blood samples for biomarker analyses should be taken prior to study drug administration. The time and date of these samples must be accurately recorded. 11. The study drug administered at Visits 1 and 2 (single-blind run-in period) is placebo for all subjects.
- The baseline EGD and biopsy can be performed within 12 days before Visit 2.
- 13. The final EGD and biopsy can be collected within 7 days before Visit 15. A final or early termination EGD and biopsy are required for all subjects. Subjects with early termination should undergo the EGD and biopsy unless a medical condition precludes it, at the Investigator's discretion.
- 14. Subjects are required to answer the stool frequency question (stools of Type 6 or 7 on BSFS) daily before bedtime in the eDiary.
- 15. The CeD PRO is captured daily in the eDiary after the last meal of the day before the subject goes to bed.
- Subjects are instructed to record PGIC and PGIS every other week in the eDiary.
- 17. Treatment-emergent adverse events are collected from the first dose of the post-randomization study drug administration (Visit 3) through the final visit. Between signing the informed consent form and the first dose of study drug (including the single-blind run-in period), only AEs related to study procedures and SAEs will be recorded.

11.2 PCI criteria for Hematology, Serum Chemistry, Urinalysis

		C	conventional Uni	its	SI Units					
Test Name	Sex	Reference Range	Units	PCI Criteria	Reference Range	Units	PCI Criteria			
Hematology			1							
	М	13.5 – 17.5	g/dL	< 8.1 or > 20	135 - 175	g/L	< 81 or > 200			
Hemoglobin	F	12.0 – 15.5	g/dL	< 8.1 or > 20	120 - 155	g/L	< 81 or > 200			
Hemoglobin				2 point decrease from baseline			20 point decrease from baseline			
White Cell Count		4.0 – 11.0	x10E3/uL	< 2.1 or > 35	4.0 - 11.0	x10E9/L	< 2.1 or > 35			
Eosinophils (Abs)		0.0 - 0.6	x10E3/uL	>=3	0.0 - 0.6	x10E9/L	>=3			
Neutrophils (Abs)		1.5 - 7.7	x10E3/uL	<1	1.5 - 7.7	x10E9/L	<1			
Platelets	17	150 - 450	x10E3/uL	< 100 or > 1000	150 - 450	x10E9/L	< 100 or > 1000			
Serum Chemistry										
	М	5.9 - 8.0	g/dL	< 4.0	59 – 80	g/L	< 40			
Protein (Total)	F	6.2 - 7.9	g/dL	< 4.0	62 - 79	g/L	< 40			
	М	4.03 - 5.51	g/dL	< 2.0	40.3 – 55.1	g/L	< 20			
Albumin	F	4.02 - 5.24	g/dL	< 2.0	40.2 - 52.4	g/L	< 20			
	М	6.7 – 33.4	IU/L	>=3X ULN	6.7 – 33.4	IU/L	>=3X ULN			
ALT	F	6.6 - 22.9	IU/L	>=3X ULN	6.6 - 22.9	IU/L	>=3X ULN			
	М	12.4 – 33.0	IU/L	>= 3X ULN	12.4 – 33.0	IU/L	>= 3X ULN			
AST	F	11.8 – 25.7	IU/L	>= 3X ULN	11.8 – 25.7	IU/L	>= 3X ULN			
	М	36.1 – 124.2	ĮU/L	>= 3XULN	36.1 – 124.2	IU/L	>= 3XULN			
AP (AlkPhos)	F	35.6 - 118.3	ĮU/L	>= 3XULN	35.6 - 118.3	IU/L	>= 3XULN			
	М	0.24 - 1.49	mg/dL	>=2X ULN	4.10 - 25.48	umol/L	>=2X ULN			
Bilirubin (Total)	F	0.19 - 1.13	mg/dL	>=2X ULN	3.25 - 19.32	umol/L	>=2X ULN			

			Conventional Ur	nits		SI Units	
Test Name	Sex	Reference Range	Units	PCI Criteria	Reference Range	Units	PCI Criteria
	М	20 - 32	mmol/L	< 18 or > 40	20 - 32	mmol/L	< 18 or > 40
Bicarbonate	F	19 - 29	mmol/L	< 18 or > 40	19 - 29	mmol/L	< 18 or > 40
	М	8.2 - 23.8	mg/dL	> 40	2.93 - 8.50	mmol/L	>14.25
BUN (Urea)	F	5.9 - 21.4	mg/dL	> 40	2.11 - 7.64	mmol/L	>14.25
	М	8.5 - 10.3	mg/dL	< 6 or > 12	2.13 - 2.58	mmol/L	< 1.5 or > 3
Calcium	F	8.5 – 10.2	mg/dL	< 6 or > 12	2.13 – 2.55	mmol/L	< 1.5 or >
	М	98 – 108	mmol/L	< 90 or > 125	90 – 108	mmol/L	< 90 or > 125
Chloride	F	99 - 107	Mmol/L	< 90 or > 125	99 - 107	mmol/L	< 90 or > 125
	М	0.63 - 1.20	mg/dL	>=1.5	55.69 - 106.08	umol/L	>=132
Creatinine	F	0.51 - 0.96	mg/dL	>=1.5	45.08 - 84.86	umol/L	>=132
Glucose		< 140	mg/dL	> 500	< 7.8	mmol/L	> 27.75
	М	1.8 – 2.2	mg/dL	<1.22 or >4.87	0.74-0.90	mmol/L	<0.5 or >2
Magnesium	F	1.7 – 2.2	mg/dL	<1.22 or >4.87	0.70 - 0.90	mmol/L	<0.5 or >2
	М	2.1 - 4.6	mg/dL	< 0.5	0.68 - 1.49	mmol/L	< 0.5
Phosphate	F	2.4 - 4.8	mg/dL	< 0.5	0.78 - 1.55	mmol/L	< 0.5
	М	3.8 - 4.9	mmol/L	< 3 or > 6	3.8 - 4.9	mmol/L	< 3 or > 6
Potassium	F	3.7 - 5.2	mmol/L	< 3 or > 6	3.7 – 5.2	mmol/L	<3 or > 6
Sodium		138 - 144	mmol/L	< 125 or > 160	138 - 144	mmol/L	< 125 or >

Urinalysis				1 1 1
Amorphous Crystals		n/a		n/a
Bacteria	Negative	Numerous	Negative	Numerous
Bilirubin	Negative	3+	Negative	3+

Crystals	Negative		Numerous	Negative		Numerous
Epithelial Cells	0-5	HPF	Numerous	0-5	HPF	Numerous
Glucose (Urine)	Negative		3+	Negative		3+
Granular Casts	None	LPF	>0	None	LPF	>0
Hemoglobin (Urine)	Negative		3+	Negative		3+
Hyaline Casts	0-1	LPF	>1	0 - 1	LPF	>1
Ketones	Negative		3+	Negative		3+
Leucocyte Esterase	Negative		3+	Negative		3+
Nitrite	Negative		3+	Negative		3+
pH	5.0 - 8.0		n/a	5.0 - 8.0		n/a
Protein (Total) (Urine)	Negative		3+	Negative		3+
RBC	0 - 2	HPF	>=10	0-2	HPF	>=10
RBC Casts	None	LPF	>0	None	LPF	>0
Sp. Gravity (SG)	1.015 - 1.025		n/a	1.015 - 1.025		n/a
Urobilinogen	Negative	l .	3+	Negative		3+
Waxy Casts	None	LPF	>0	None	LPF	>0
WBC	0 - 5	HPF	>=10	0-5	HPF	>=10
WBC Casts	None	LPF	>0	None	LPF	>0

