8.7.3 Clinical Laboratory Tests

8.7.3.1 Serum Chemistry, Hematology, Urinalysis, Pregnancy Tests

Laboratory safety variables include hematology, clinical chemistry and urinalysis panels. The complete list of laboratory tests is included in Table 4 below.

Table 4. Clinical Laboratory Tests

Serum Chemistry (Units)	Hematology (Units)	Urinalysis
ALT (IU/L)	Basophils (109/L)	Appearance
AST (IU/L)	Basophils/Leukocytes (%)	Bilirubin
Albumin (g/L)	Eosinophils (109/L)	Color
Alkaline Phosphatase (IU/L)	Eosinophils/Leukocytes (%)	Glucose
Total Bilirubin (umol/L)	Mean cell hemoglobin (MCH)	Ketones
Direct Bilirubin (umol/L)	Mean Corpuscular HGB Concentration	Leukocyte Esterase
Calcium (mmol/L)	(g/L)	Nitrite
Carbon Dioxide (mmol/L)	Mean Corpuscular Hemoglobin (fmol)	Occult Blood
Chloride (mmol/L)	Mean Corpuscular Volume (fL)	pH
Creatinine (umol/L)	Hematocrit (%)	Protein
Glucose (mmol/L)	Hemoglobin (g/L)	Specific Gravity
Magnesium (mmol/L)	Lymphocytes (109/L)	Urobilinogen
Phosphorus (mmol/L)	Lymphocytes/Leukocytes (%)	
Potassium (mmol/L)	Monocytes (109/L)	Urine Microscopic
Total Protein (g/L)	Monocytes/Leukocytes (%)	
Sodium (mmol/L)	Neutrophils (109/L)	Urine pregnancy
Urea Nitrogen (mmol/L)	Neutrophils/Leukocytes (%)	test
	Platelets (109/L)	
	Red Blood Cell Count (1012/L)	

	White Blood Cell Count (109/L)	
--	--------------------------------	--

Clinical laboratory parameters will be obtained at times indicated in the SoA in Appendix 11.1. Cutoff values considered to be potentially clinically important (PCI) for selected laboratory tests are outlined in Appendix 11.2.

A summary of subjects meeting any of the PCI criteria for post-baseline laboratory measurements will be provided by treatment group. All clinical laboratory test results will be provided in data listings with PCI criteria flagged.

Separate data listings for urine and serum pregnancy tests will be provided in female subjects of childbearing potential.

Potential Hy's law (ALT or AST > 3 x ULN concurrent with total bilirubin > 2 x ULN at the same visit) will be summarized by treatment group and listed. eDish plots will be used to present subjects potentially meeting Hy's law.

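### The phosphate PCI limit in SAP Appendix 11.2 is printed as the same number in mg/dL and mmol/L, so at least one of the two entries is wrong by about 3.1-fold

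*SAP*

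**What the plan says.** SAP 8.7.3.1 refers to Appendix 11.2 for the laboratory thresholds: "values considered to be potentially clinically important (PCI) for selected laboratory tests are outlined in Appendix 11.2". It then states their use: "A summary of subjects meeting any of the PCI criteria for post-baseline laboratory measurements will be provided by treatment group". Laboratory listings carry the same flags. PCI laboratory changes are among the secondary safety endpoints in SAP 3.2.

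Appendix 11.2 gives each threshold twice, once in conventional and once in SI units. For phosphate:

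- Female: "Phosphate F 2.4 - 4.8 mg/dL < 0.5 0.78 - 1.55 mmol/L < 0.5"
- Male, the row directly above: "2.1 - 4.6 mg/dL < 0.5 0.68 - 1.49 mmol/L < 0.5"

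Table 4 in SAP 8.7.3.1 lists the analyte in SI units, as "Phosphorus (mmol/L". No sentence in the SAP says which column of Appendix 11.2 governs the flag.

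**The concern.** In each phosphate row the reference range changes number between columns, as it must when the unit changes, but the PCI threshold does not. The two printed thresholds therefore describe different concentrations, and at least one looks like a number carried across without conversion.

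What is at stake is the meaning of the phosphate flag. Relative to the lower reference limit, the mg/dL entry is a far stricter criterion than the mmol/L entry. A value lying between the two is PCI under one and not under the other. Since the planned summary counts subjects who meet PCI criteria, one wrong limit can change a subject's status in it. If the discrepancy is first noticed after unblinding, the safety threshold would have to be chosen with the data in view.

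**Working it through.** **Inputs**, all from SAP Appendix 11.2:

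- Male range: 2.1–4.6 mg/dL and 0.68–1.49 mmol/L
- Female range: 2.4–4.8 mg/dL and 0.78–1.55 mmol/L
- PCI threshold: below 0.5 in both columns, both sexes

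**Step 1. Conversion factor implied by the ranges** (mg/dL limit ÷ mmol/L limit):

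- Male: 2.1/0.68 = 3.088 and 4.6/1.49 = 3.087
- Female: 2.4/0.78 = 3.077 and 4.8/1.55 = 3.097
- Mean: 3.087, or 1/3.087 = 0.324 mmol/L per mg/dL

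**Step 2. Could rounding explain it?** Moving each printed limit by half its last digit in the least favourable direction gives 2.99 at the lowest, (2.1 − 0.05)/(0.68 + 0.005), and 3.19 at the highest, (2.1 + 0.05)/(0.68 − 0.005). The thresholds imply 0.5/0.5 = 1.0, which is far outside that interval.

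**Step 3. Convert each printed threshold:**

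- 0.5 mg/dL ÷ 3.087 = 0.162 mmol/L
- 0.5 mmol/L × 3.087 = 1.54 mg/dL

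The band in dispute runs from 0.16 to just under 0.5 mmol/L (0.5 to just under 1.54 mg/dL). For example, 0.3 mmol/L is 0.3 × 3.087 = 0.93 mg/dL, which is PCI by the SI entry and not PCI by the conventional entry.

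**Step 4. Threshold as a share of the lower reference limit:**

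| | mg/dL entry | mmol/L entry |
|---|---|---|
| Male | 0.5/2.1 = 24% | 0.5/0.68 = 74% |
| Female | 0.5/2.4 = 21% | 0.5/0.78 = 64% |

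**Step 5. Is this a convention of the table?** The same comparison was made for every row whose units differ between columns and whose cut-off is a number (conventional ÷ SI):

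| Analyte | Factor from ranges | Factor from PCI limits |
|---|---|---|
| Hemoglobin, total protein, albumin | 0.1 | 0.1 |
| Urea | 2.80 | 40/14.25 = 2.81 |
| Calcium | 3.99 | 6/1.5 = 4.00 |
| Creatinine | 0.0113 | 1.5/132 = 0.0114 |
| Glucose | 17.9 | 500/27.75 = 18.0 |
| Magnesium | 2.43–2.44 | 1.22/0.5 = 2.44 |
| **Phosphate** | **3.08–3.10** | **0.5/0.5 = 1.0** |

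The calcium row ("8.5 - 10.3 mg/dL < 6 or > 12 2.13 - 2.58 mmol/L < 1.5 or > 3") and the magnesium row ("<1.22 or >4.87 0.70 - 0.90 mmol/L <0.5 or >2") show thresholds that were properly converted. Phosphate is the only mismatch. A fault in reading the PDF is unlikely, because the same value stands in both sex rows and the neighbouring cells are intact.

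**The case against.** The best reply is that Table 4 largely settles which column is used. It lists phosphorus in mmol/L, and the other chemistry analytes whose units differ between the columns of Appendix 11.2 also appear there in SI units. The appendix is cited in the same section, so a programmer would naturally apply the SI cell. That cell also flags more: anything below 0.16 mmol/L is below 0.5 mmol/L too, so nothing caught by the conventional entry would be lost.

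Much of this stands. A reader might infer from the two columns that the flag is simply open to whichever unit someone happens to pick. The documents do not support that, because Table 4 points to SI. What the reply does not settle is the limit itself. Reporting in mmol/L does not show that 0.5 mmol/L was the limit meant. If the mg/dL figure was meant, SI programming would flag values between 0.16 and 0.5 mmol/L that the sponsor did not intend to flag. If the mmol/L figure was meant, anyone working from the conventional column would miss those same values. The SAP also has no sentence that fixes the column.

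It is also fair to say that the effect is small. The outputs are a descriptive summary and listings. All laboratory results are listed whether flagged or not, and Protocol 8.3.4 has the investigator review each laboratory report and judge whether a change is an adverse event. Phosphate is not among the laboratory exclusions in Protocol 5.2, and no stopping rule refers to it.

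**Conclusion.** The inconsistency is real and is proved by the table's own figures. The two phosphate limits differ about 3.1-fold in both sex rows, and at least one is wrong. The documents do not show which, and this review takes no position on it.

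The size is modest: one descriptive flag behind a secondary safety endpoint, with no effect on efficacy, eligibility or stopping. The number of subjects with a value in the disputed band cannot be estimated from the documents. The description of the band as 0.16 to just under 0.5 mmol/L assumes that one of the two printed limits is the intended one.

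A reader might also infer that the Laboratory Manual contains the same error, since Protocol 8.3.4 says the cut-offs will be set out there as well as in the SAP. The Manual is not among the documents, so agreement with it is something to check and not a demonstrated defect.

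**What to change.** 1. Have the sponsor's medical reviewer confirm the intended phosphate limit.
2. Derive the other column from it with the table's own factor (about 0.324 mmol/L per mg/dL), and correct both the male and the female row.
3. Add one sentence to SAP 8.7.3.1 stating which unit column governs PCI flagging.
4. Check that the Laboratory Manual carries the same limit.

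The cost is one medical confirmation, at least two table cells (one per sex) and one sentence. No data collection or model changes. It is best done before unblinding, so that the threshold is not chosen after the data have been seen.
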